**Table 5.1-3: Study Evaluations - Open-Label Period (IM101611)**

Study Day a	Day 169 b	Day 197	Day 225	Day 253	Day 281	Day 309	Day 337	Day 365	
Procedure		Wk 28	Wk 32 (Phone)	Wk 36/ Mo 9	Wk 40 (Phone)	Wk 44	Wk 48 (Phone)	Wk 52 Mo 12 or OL ET	Notes
Outcomes Research Assessments									
HAQ-DI		X		X		X		X	IMACS Core Component
PROMIS Fatigue				X				X	
SF-36				X				X	

a All visits and procedures must occur within  $\pm 3$  days of the expected visit

b Same visit as Double-blind Day 169

c If a subject does not consent to the use of their samples for additional research, their samples will be discarded after all protocol-specified testing has been completed (not to exceed 5 years)

**Table 5.1-4: Post-Study Drug Efficacy Visit (Discontinued Subjects Between Baseline and Wk 24)**

Visit (± 14 days)	169 Days (24 Weeks) Post-Baseline	Notes
Safety Assessments		
Vital Signs	X	
Adverse Event Monitoring	X	
██████████	█	
Pulmonary Function Testing	X	For subjects with ILD (See Section 5.3.6)
Efficacy Assessments		
Physician Global Assessment	X	IMACS Core Component
Subject Global Assessment	X	IMACS Core Component
Manual Muscle Test (MMT-8)	X	IMACS Core Component
Myositis Disease Activity Assessment Tool (MDAAT)	X	IMACS Core Component
Myositis Function Index (FI-2)	X	
Myositis Damage Index	X	
Cutaneous Disease Activity Index (CDASI)	X	
Muscle biopsy (optional - for histopathology and RNA)	X	
Imaging Assessments		
HRCT Chest	X	For subjects with clinically active or relevant ILD or anti-synthetase syndrome. (See Section 5.3.7.2)
██████████	█	████████████████████
Outcomes Research Assessments		
HAQ-DI	X	IMACS Core Component
PROMIS Fatigue	X	
SF-36	X	

**Table 5.1-4: Post-Study Drug Efficacy Visit (Discontinued Subjects Between Baseline and Wk 24)**

Visit ( $\pm$ 14 days)	169 Days (24 Weeks) Post-Baseline	Notes
Laboratory Assessments		
Hematology Panel	X	
Chemistry Panel	X	IMACS Core Component
Antibody Panels	X	
Complement (C3, C4, CH50)	X	
[REDACTED]	■	
PBMCs (Peripheral Blood Mononuclear Cells) a	X	(US sites only)

a If a subject does not consent to the use of their samples for additional research, their samples will be discarded after all protocol-specified testing has been completed (not to exceed 5 years).

**Table 5.1-5: Open Label Extension for Japan**

Study Day a	Day 365 b	Day 393	Day 421	Day 449	Day 477	Day 505	Day 533	
Procedure	Wk 52/ Mo 12	Wk 56 (Phone)	Wk 60	Wk 64/ Mo 15 (Phone)	Wk 68	Wk 72 (Phone)	Wk 76/ Mo 18 or OL-EXT ET	Notes
Study Administration								
Call IVRS			X		X		X	
Dispense diary cards	X		X		X			
Collect and review diary cards			X		X		X	
Dosing of weekly abatacept	X	X	X	X	X	X	X	Must be administered weekly between visits. See Section 4.5. No dose administered at the Early Termination visit
Reconciliation of abatacept			X		X		X	
Dispense urine pregnancy kits for WOCBP	X		X		X			For home use every 4 weeks
Dispense Study Drug	X		X		X			
Safety Assessments								
Vital Signs			X		X		X	
Weight			X		X		X	
Targeted Physical Examination			X		X		X	
Adverse Events Monitoring		X	X	X	X	X	X	
		■	■	■	■	■	■	
Pulmonary Function Testing							X	For subjects with ILD (See Section 5.3.6)

**Table 5.1-5: Open Label Extension for Japan**

Study Day a	Day 365 b	Day 393	Day 421	Day 449	Day 477	Day 505	Day 533	
Procedure	Wk 52/ Mo 12	Wk 56 (Phone)	Wk 60	Wk 64/ Mo 15 (Phone)	Wk 68	Wk 72 (Phone)	Wk 76/ Mo 18 or OL-EXT ET	Notes
Laboratory Assessments								
Hematology Panel			X		X		X	
Chemistry Panel			X		X		X	IMACS Core Component
Total Cholesterol and Triglycerides							X	Nothing to eat/drink, except water, for 8 hours prior to sample collection
Urine pregnancy test		X	X	X	X	X	X	Testing performed locally on WOCBP subjects only
Pharmacokinetic (PK) Sampling in Blood							X	All samples must be collected prior to dosing. See Section 5.5.1 for sub-study sample times
Complement (C3, C4, CH50)							X	
								
Efficacy Assessments								
Physician Global Assessment c			X		X		X	IMACS Core Component
Subject Global Assessment c			X		X		X	IMACS Core Component
Manual Muscle Test (MMT-8) c			X		X		X	IMACS Core Component

**Table 5.1-5: Open Label Extension for Japan**

Study Day a	Day 365 b	Day 393	Day 421	Day 449	Day 477	Day 505	Day 533	
Procedure	Wk 52/ Mo 12	Wk 56 (Phone)	Wk 60	Wk 64/ Mo 15 (Phone)	Wk 68	Wk 72 (Phone)	Wk 76/ Mo 18 or OL-EXT ET	Notes
Myositis Disease Activity Assessment Tool (MDAAT) c			X		X		X	IMACS Core Component
Myositis Function Index (FI-2) c							X	
Myositis Damage Index c							X	
Cutaneous Disease Activity Index (CDASI) c							X	For subjects with DM
Imaging Assessments								
HRCT Chest							X	For subjects with clinically active or relevant ILD or anti-synthetase syndrome. (See Section 5.3.7.2).
Outcomes Research Assessments								
HAQ-DI c			X		X		X	IMACS Core Component

a All visits and procedures must occur within  $\pm 3$  days of the expected visit

b Same visit as Open-Label Period Day 365

c Assessments may be recorded on paper if the electronic tablet (ePRO) is unavailable/not functioning for transmission of the data.

**Table 5.1-6: Long Term Open-Label Period (all countries except U.S. and the Czech Republic)**

	Day 1 (same day as last visit in OL Period)	Phone Visits (Day 29, 57, 113, 141, 197, 225, 281, 309, and 337)	Quarterly Visits (Days 85 and 253)	6 Months Visits (Day 169 and 365)	Phone Visits (Day 393, 421, 477, 505, 561, 589, 645, 673, and 701)	Quarterly Visits (Days 449 and 617)	6 Months Visits (Day 533 and 729)	Phone Visits (Day 757, 785, 841, 869, 925, 953, 1009, 1037, and 1065)	Quarterly Visits Visit (Day 813 and 981)	6 Month Visit (Day 897)	Day 1093/ET Visit	Notes
Study Administration												
Informed Consent	X											
Enroll subject in the 3 Year Extension Period through IWRS	X											
Dispense pregnancy kits for home use to WOCBP	X		X	X		X	X		X	X		Sufficient pregnancy kits should be dispensed to subjects to allow for pregnancy testing every 4 weeks.
Dispense SC abatacept and diary kits	X		X	X		X	X		X	X		Sufficient SC abatacept should be dispensed to allow for weekly SC dosing.
Review of diary cards		X	X	X	X	X	X	X	X	X	X	
Dosing of SC Abatacept	X	X	X	X	X	X	X	X	X	X		SC Abatacept will injected weekly.
Reconciliation of SC Abatacept			X	X		X	X		X	X	X	
Safety Assessments												
Targeted Physical Examination			X	X		X	X		X	X	X	

**Table 5.1-6: Long Term Open-Label Period (all countries except U.S. and the Czech Republic)**

	Day 1 (same day as last visit in OL Period)	Phone Visits (Day 29, 57, 113, 141, 197, 225, 281, 309, and 337)	Quarterly Visits (Days 85 and 253)	6 Months Visits (Day 169 and 365)	Phone Visits (Day 393, 421, 477, 505, 561, 589, 645, 673, and 701)	Quarterly Visits (Days 449 and 617)	6 Months Visits (Day 533 and 729)	Phone Visits (Day 757, 785, 841, 869, 925, 953, 1009, 1037, and 1065)	Quarterly Visits Visit (Day 813 and 981)	6 Month Visit (Day 897)	Day 1093/ET Visit	Notes
Adverse Event Monitoring		X	X	X	X	X	X	X	X	X	X	
██████████		█	█	█	█	█	█	█	█	█	█	
Laboratory Testing												
Hematology Panel				X			X			X	X	
Chemistry Panel				X			X			X	X	

**Table 5.1-7: Post-Treatment Follow-Up Period (only performed for subjects that discontinue study treatment and do not start Post-Study Drug Program (PSDP) or commercial abatacept)**

Visit (± 14 days)	85 Days after Last Dose	169 Days after Last Dose	Notes
Safety Assessments			
Vital Signs	X	X	
Adverse Event Monitoring	X	X	
[REDACTED]	■	■	
Laboratory Assessments			
Urine pregnancy test	X	X	Testing performed locally on WOCBP subjects only
[REDACTED]	■	■	[REDACTED]
[REDACTED]	■	■	[REDACTED]

[REDACTED]

### **5.1.1 Retesting During Screening or Lead-in Period / Rescreening**

#### Retesting

Retesting of laboratory parameters and/or other assessments within any single Screening period will be permitted (in addition to any parameters that require a confirmatory value).

Any new result will override the previous result (i.e., the most current result prior to Randomization) and is the value by which study inclusion will be assessed, as it represents the subject's most current, clinical state.

Laboratory parameters and/or assessments that are included in [Table 5.1-1](#), Screening Procedural Outline may be repeated in an effort to find all possible well-qualified subjects. The Medical Monitor can be consulted if needed to discuss whether repeat testing of any particular parameter is clinically relevant.

#### Rescreening

Subjects that are screen failures may be considered for re-screening if the investigator feels a change in status may render the subject eligible. Medical monitor approval is required if screen failure was related to safety concern. Rescreens are not permitted within the four weeks after signing the first informed consent.-The subject will need to sign a new informed consent and be re-enrolled with a new subject number via the IVRS. Some tests, such as chest X-ray, may not need to be repeated if they were performed within the protocol defined window.

#### **5.1.1.1 Study Drug Administration Windows**

SC injections of study medication may be administered  $\pm 3$  days of the target day. Subjects who miss the dose window should skip the SC injection and wait until the next targeted administration day.

If abnormal laboratory test results or clinical AEs indicate toxicity that, in the judgment of the investigator, could place the subjects at risk, study medication administration should be withheld. Subjects may receive further study medication only if resolution of the AE or abnormal laboratory finding is documented or, at a minimum, the subject's status returns to what it was at baseline. The investigator can contact the BMS Study Medical Monitor to discuss as needed.

#### **5.1.2 Order of Study Assessments**

It is strongly encouraged that study assessments be performed in the following order:

- 1) Patient reported outcomes (PROs) questionnaires
- 2) AE collection
- 3) Vital signs
- 4) Muscle strength assessments
- 5) Other investigator assessments
- 6) Blood draws
- 7) Study drug administration (when applicable)

## 5.2 Study Materials

- Diary cards to record SC weekly dosing administration and the monthly pregnancy test results for WOCBPs (mandatory)
- Written instructions on how to use the SC syringes
- eCRF instructions
- Pregnancy Surveillance Forms
- Source documents (paper or electronic device)
- Drug Inventory binder (optional)
- Interactive Voice Response System (IVRS) worksheets
- Laboratory test kits for all required laboratory testing
- Cooler bags and gel packs will be provided to assist subjects in transporting study drug
- Sharps containers will be provided to assist subjects in disposing of used SC syringes
- Tote bags to transport cooler bags, sharp containers and study drug
- For WOCBP urine pregnancy kits/instructions will be provided to be used between office visits.
- HRCT and MRI Imaging Manuals
- Actigraphy device Manuals
- Metronome, wrist weights, step stool

## 5.3 Safety Assessments

On Day 1, the results of all assessments must be reviewed to assure that eligibility requirements are met before contacting the Central Randomization System for the subject's randomization assignment.

Subjects who terminate treatment early should complete the appropriate Early Termination Visit (Table 5.1-2, Table 5.1-3, Table 5.1-5, and Table 5.1-6) and the Post Treatment Follow-up Visits (Table 5.1-7). The Early Termination Visit should be as soon as possible after the last dose of study medication.

All assessments should be performed or administered prior to study drug administration unless otherwise indicated.

Only data for the procedures and assessments specified in this protocol should be submitted to BMS on a case report form. Additional procedures and assessments may be performed as part of the standard of care; however, data for these assessments should remain in the subject's medical record and should not be provided to BMS, unless specifically requested from BMS.

Only results of central laboratory assessments relevant to clinical care will be sent to the sites (Section 5.3.5). All other clinical assessments done as part of this study, including PFTs, HRCT, MRI of the thighs and muscle biopsies will not be read centrally for return to the site. These must be read locally following usual and customary practices for clinical assessments and reviewed by

investigators as required by the protocol for safety assessments (ie, PFT and HRCT) or as deemed necessary by investigators for those not required by the protocol (ie, MRI or muscle biopsy). Reports generated from central analysis of these will not be clinical in nature and will not be sent to sites for review.

Subjects who have clinically active or relevant Interstitial Lung Disease (ILD) as determined by the investigator prior to randomization must undergo pulmonary function testing (PFT) and imaging by High Resolution CT scan (HRCT). The target populations are described and the testing are outlined in [Section 5.3.6](#) and [Section 5.3.7.2](#), respectively.

### **5.3.1 Physical Examination**

Physical examinations preferably should be performed by a qualified physician or Doctor of Medicine (MD). Where permitted by local practice and guidelines a qualified Doctor of Osteopathy (DO), Physician Assistant (PA), or Nurse Practitioner (NP) may perform the physical examination.

The physical examination should include examination of the heart, lungs, abdomen, the lymph nodes, liver, spleen and skin. A physical examination may note any changes in the subject's condition (body systems) since the last assessment and does not preclude examination of any other body systems as clinically indicated. Any new findings after Day 1 should be reported as (S)AE.

### **5.3.2 Physical Measurements**

Weight and height is to be recorded at screening. Weight is to be recorded as noted in [Table 5.1-2](#), [Table 5.1-3](#), and [Table 5.1-5](#), thereafter.

### **5.3.3 Vital Signs**

Vital signs (seated blood pressure, heart rate, and temperature) will be recorded during every office visit and prior to dose administration, when applicable. Blood pressure and heart rate should be measured after the subject has been seated quietly for at least 5 minutes.

### **5.3.4 TB Screening**

A chest X-ray and physical examination are considered part of the process to assess a subject's eligibility. In addition to a chest X-ray that does not show any evidence or suspicion of latent TB, a tuberculin test will be performed and interpreted according to local country Health Authorities and/or Medical Society guidelines. Some guidelines have specific recommendations for subjects who are to receive biologics or immunosuppressant therapies (eg, RA experience with biologic agents), (outside the US sites, local guidelines endorsed by medical societies on PPD testing in subjects with RA being treated with biologics may also apply) or who are immunocompromised and who have had prior BCG vaccination(s). Tuberculin skin testing is not contraindicated for persons who have been vaccinated with BCG. An interferon gamma release assay (eg, QuantiFERON Gold or Tspot/ELISpot) is an acceptable alternative when skin testing for tuberculosis (ie, PPD) is not appropriate. TB screening test may be performed by qualified personnel at the central laboratory or by a qualified local laboratory. If TB test has been performed

within 4 weeks prior to informed consent and clear documentation is available, the test result may be used to screen for eligibility.

### **5.3.5 Laboratory Assessments**

All laboratory assessments will be analyzed centrally except where noted.

Blood and/or urine samples will be obtained at all visits noted in Time and Events Schedule. Any laboratory test result that the investigator considers clinically relevant should be recorded on the appropriate Adverse Event page of the CRF (see [Appendix 2](#)).

#### **5.3.5.1 Hematology Panel**

- Hemoglobin
- Total WBC count, including differential
- Platelet count

#### **5.3.5.2 Chemistry Panel**

- Sodium
- Potassium
- Chloride
- Total Protein
- Albumin
- Calcium
- Phosphorus
- Glucose
- Aldolase
- Creatinine
- Blood urea nitrogen (BUN)
- Total bilirubin
- Alanine aminotransferase (ALT)
- Aspartate aminotransferase (AST)
- Gamma-glutamyltransferase (GGT)
- Alkaline phosphatase
- LDH
- Creatine kinase (CK)

#### **5.3.5.3 Antibody Panels**

- Quantitative Immunoglobulins (IgG, IgA, IgM)
- Anti-nuclear antibody (ANA) panel
- Myositis-specific autoantibodies (eg. Jo-1, PL-12, PL-7, OJ, EJ, SRP, Mi-2, TIF1- $\gamma$ , MDA5, NXP2)
- Myositis-associated autoantibodies (eg. PM/Scl, Ku, SS-A, U1 RNP, U2 snRNP, fibrillarin U3 RNP)

#### **5.3.5.4 Complement**

- C3
- C4
- CH50

### **5.3.5.5 Urinalysis**

- pH
- Protein
- Glucose
- Blood

### **5.3.5.6 Hepatitis Screen**

- Hepatitis B surface antigen, hepatitis B core antibody. If positive, reflex Hepatitis B viral DNA testing must be performed. Where required by local regulations or standard practice Hepatitis B viral DNA testing also must be performed on Hepatitis B surface antibody (HBsAb)-positive subjects.
- Hepatitis C antibody. If positive, reflex HCV RNA testing must be performed

#### **NOTE: For Japan only subjects**

- Hepatitis B surface antigen, hepatitis B core antibody (hepatitis B surface antibody, where required by local guidelines). If negative HBs antigen but positive anti-HBc antibody or positive anti-HBs antibody, reflex Hepatitis B viral DNA testing must be performed.

### **5.3.5.7 Pregnancy Tests**

Urine/serum pregnancy tests (minimum sensitivity 25 IU/L of  $\beta$ -HCG) must be performed, with a negative result, for all WOCBP within 24 hours prior to dosing for visits specified in [Table 5.1-2](#), [Table 5.1-3](#), [Table 5.1-5](#), [Table 5.1-6](#) and every 4 weeks in the Follow up period, [Table 5.1-7](#). Urine tests are the preferred method and must be performed unless serum is required by local regulations. A serum test must be performed for confirmation of any positive urine test result. Urine tests can be processed locally and can be self-administered by the subject between office visits, if permitted by local regulations. If any female subject becomes pregnant, she will stop receiving study treatment immediately and enter the Post Treatment Follow-up Period. A pregnancy surveillance form will be completed and submitted to Bristol-Myers Squibb. Serum pregnancy tests will be processed centrally.

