Subjects who discontinue treatment with study medication during the Double-blind Period will complete the Early Termination visit (which is the same visit as Day 169 visit) (See [Table 5.1-2](#)). These subjects must also return on the previously scheduled Double-blind Period Day 169 to complete the Post-Study Drug Efficacy Visit (see [Table 5.1-4](#)). The purpose of this visit is to assess all aspects of disease activity to ascertain the impact of study participation for regulatory review. Subjects must also complete 2 follow-up visits (85 and 169 days after the last dose) during the 24 week post-treatment follow-up period, to perform safety and laboratory assessments (See [Table 5.1-7](#) Post-Treatment Follow-Up Period). This Period begins on the day of the Early Termination visit and applies only to subjects who do not start commercial abatacept therapy.

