### 3) Age and Reproductive Status

- a) Men and Women, age  $\geq 18$  or age of majority
- b) Women of childbearing potential (WOCBP) must have a negative serum or urine pregnancy test (minimum sensitivity 25 IU/L or equivalent units of HCG) within 24 hours prior to the start of study drug.
- c) Women must not be breastfeeding
- d) WOCBP must agree to follow instructions for method(s) of contraception for the duration of treatment with study drug(s) (abatacept) plus 5 half-lives of study drug (70 days) plus 30 days (duration of ovulatory cycle) for a total of 100 days post-treatment completion
- e) Men who are sexually active with WOCBP must agree to follow instructions for method(s) of contraception for the duration of treatment with study drug(s) (abatacept) plus 5 half-lives of the study drug (70 days) plus 90 days (duration of sperm turnover) for a total of 160 days post-treatment completion. In addition, male subjects must be willing to refrain from sperm donation during this time.
- f) Azoospermic males are exempt from contraceptive requirements. WOCBP who are continuously not heterosexually active are also exempt from contraceptive requirements, and still must undergo pregnancy testing as described in this section.

Investigators shall counsel WOCBP, and male subjects who are sexually active with WOCBP, on the importance of pregnancy prevention and the implications of an unexpected pregnancy. Investigators shall advise on the use of highly effective methods of contraception ([Appendix 1](#)), which have a failure rate of  $< 1\%$  when used consistently and correctly. It is expected that investigators will refer to the Product Insert, as well as local regulations and guidelines for prevention of pregnancy appropriate for the standard background treatment being used by individual subjects.

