### **6.4 Pregnancy**

If, following initiation of the study drug, it is subsequently discovered that a study subject is pregnant or may have been pregnant at the time of study exposure, including during at least 5 half-lives after product administration, the investigator must immediately notify the Sponsor or designee of this event and complete and forward a Pregnancy Surveillance Form to BMS Designee within 24 hours of awareness of the event and in accordance with SAE reporting procedures described in [Section 6.1.1](#).

In most cases, the study drug will be permanently discontinued in an appropriate manner (eg, dose tapering if necessary for subject safety). Please call the Sponsor or designee within 24 hours of awareness of the pregnancy.

Protocol-required procedures for study discontinuation and follow-up must be performed on the subject.

The investigator must immediately notify the Sponsor or designee of this event and complete and forward a Pregnancy Surveillance Form to Sponsor or designee within 24 hours of awareness of the event and in accordance with SAE reporting procedures described in [Section 6.1.1](#).

Follow-up information regarding the course of the pregnancy, including perinatal and neonatal outcome and, where applicable, offspring information must be reported on the Pregnancy Surveillance Form.

Any pregnancy that occurs in a female partner of a male study participant should be reported to Sponsor or designee. In order for BMS to collect any pregnancy surveillance information from the

female partner, the female partner must sign an informed consent form for disclosure of this information. Information on this pregnancy will be collected on the Pregnancy Surveillance Form.

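### Protocol Section 5.3.5.7 requires pregnancy tests every 4 weeks after treatment stops, but the table it cites (5.1-7) marks only two, neither of which can fall within 70 days of the last dose

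*Protocol*

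**What the plan says.** - **Protocol Section 5.3.5.7 (Pregnancy Tests).** Urine or serum tests are mandatory for all WOCBP at the visits in the treatment-period tables and "every 4 weeks in the Follow up period", with Table 5.1-7 cited for follow-up. Urine tests may be done by the subject between office visits where local rules allow.
- **Protocol Table 5.1-7 (Post-Treatment Follow-Up Period).** There are two visits, "85 Days after Last Dose" and "169 Days after Last Dose", each ±14 days. The urine pregnancy test is marked at both, with the note "Testing performed locally on WOCBP subjects only". Some rows are blacked out. The legible ones show no interim contact, home test or kit dispensing.
- **Protocol Section 3.1.6.** Follow-up lasts 24 weeks. It is required only of subjects who stop study treatment and do not start abatacept from another source.
- **Protocol Section 3.3.1, item 3 (Age and Reproductive Status).** WOCBP must use contraception during treatment "plus 5 half-lives of study drug (70 days) plus 30 days (duration of ovulatory cycle) for a total of 100 days post-treatment completion".
- **Protocol Section 6.4.** Reporting covers a pregnancy discovered later if the subject may have been pregnant during exposure, "including during at least 5 half-lives after product administration".
- **Protocol Section 5.2.** Study materials include pregnancy kits for use between office visits and mandatory diary cards that record monthly pregnancy test results.

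**The concern.** A mandatory requirement and the schedule it cites give different test frequencies. Table 5.1-7 is the current number of the follow-up table, so this is not a stale cross-reference. Nor is it the protocol's usual shorthand. Tables 5.1-3 and 5.1-5 mark tests at the phone visits as well as the office visits and dispense kits for 4-weekly home use, and Table 5.1-6 dispenses enough kits for testing every 4 weeks. The follow-up table has no such row in its legible part, and none of these three tables dispenses kits at its final or early termination visit.

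Sites commonly schedule from the table. If they do so here, they will depart from the text, and practice may differ between sites. The stake is safety surveillance: the protocol wants pregnancies reported when exposure may have continued for 5 half-lives after dosing, and reporting starts only when someone becomes aware of the pregnancy.

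**Working it through.** **Inputs.** Follow-up length 24 weeks (Section 3.1.6); test interval 4 weeks (Section 5.3.5.7); table visits at Days 85 and 169 after the last dose, ±14 days (Table 5.1-7); 5 half-lives = 70 days, plus 30 days = 100 days (Section 3.3.1, item 3); 56 days ≈ 4 half-lives (SAP Section 7.4.1.1).

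**1. The plan's own exposure window.** From the SAP, one half-life ≈ 56 / 4 = 14 days, so 5 × 14 = 70 days and 70 + 30 = 100 days. Both protocol figures are reproduced.

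**2. Number of tests.** 24 / 4 = 6, at about Days 28, 56, 84, 112, 140 and 168 after the last dose. Table 5.1-7 marks 2. Its Days 85 and 169 match the third and sixth of these to within a day, so four tests in the text have no counterpart in the table.

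**3. Position of the first table test.**

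| First visit | Day after last dose | Relative to Day 70 | Relative to Day 100 |
|---|---|---|---|
| Earliest | 85 − 14 = 71 | 1 day after | 29 days before |
| Nominal | 85 | 15 days after | 15 days before |
| Latest | 85 + 14 = 99 | 29 days after | 1 day before |

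**4. Tests inside each window.**

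| Window | By the text | By Table 5.1-7 |
|---|---|---|
| 70 days | 2 (Days 28, 56) | 0, anywhere in the visit window |
| 100 days | 3 (Days 28, 56, 84) | 1 |

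**5. Possible delay in detection, at nominal dates.** A pregnancy first detectable at Day 28 would be found 85 − 28 = 57 days later under the table. One first detectable at Day 56 would be found 85 − 56 = 29 days later. One detectable only by Day 84 would be found 85 − 84 = 1 day later. The loss is therefore concentrated in pregnancies that begin early in follow-up.

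**6. A related gap for double-blind discontinuers.** Under Section 3.5, if a Day 85 or Day 169 follow-up visit falls within ±14 days of the Week 24 Post-Study Drug Efficacy Visit, only the immunogenicity and pharmacokinetic samples from Table 5.1-7 are taken with that visit. The legible rows of Table 5.1-4, which governs the efficacy visit, show no pregnancy test. At nominal dates the Day 85 visit overlaps when the last dose was near study day 169 − 85 = 84, that is, days 70 to 98. The Day 169 visit overlaps when the last dose was within the first 14 days. Read literally, such a subject keeps only one of the two table tests.

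**The case against.** Three stronger conclusions are tempting, and the documents do not support them.

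**That sites cannot comply.** Section 5.3.5.7 permits self-testing between visits, and Section 5.2 lists kits and monthly test diaries without limiting them to a treatment period. Office tests in the table and home tests from the text can be read as complementary. This stands: a site can meet the text. What remains is that Table 5.1-7 neither schedules the home tests nor shows who supplies the kits once treatment has ended.

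**That nobody is tested within 70 days of the last dose.** Tables 5.1-2, 5.1-3 and 5.1-5 mark a urine test at the end-of-period or early termination visit. Section 5.3 asks for the early termination visit as soon as possible after the last dose, and Section 4.5.1 puts the last doses of these periods about a week before the Week 24, 52 and 76 visits. The 70-day statement therefore holds only for tests in Table 5.1-7. No such test is visible at the final visit in Table 5.1-6, so this reassurance is weaker for the long-term extension.

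**That exposure pregnancies would go unfound.** Section 6.4 looks back from discovery and sets no detection deadline at Day 70. A continuing pregnancy that began before Day 70 can still be found at Day 85 and reported. Even testing every 4 weeks would not find a conception on Days 57 to 70 until about Day 84. A first test after Day 70 is not in itself a defect; later detection is the supportable consequence.

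The redactions also matter. The absence of a kit row can be asserted only for the legible part of Table 5.1-7, although the pregnancy-test row itself is legible.

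**Conclusion.** The inconsistency is real. The text implies about 6 follow-up tests and the table it cites gives 2. None of the table tests can fall within 70 days of the last dose, even at the earliest edge of the visit window, and one falls within 100 days. A site following the table alone would not meet the text. Some exposure pregnancies could be detected later, by up to about 8 weeks at nominal dates (57 days), and early losses could be missed.

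This rests on three assumptions: 4-weekly testing is counted from the last dose, the blacked-out rows of Table 5.1-7 contain no home-test or kit provision, and the site adds nothing to the table. The scope is limited to WOCBP who stop treatment and do not start abatacept from another source. No efficacy analysis is affected. The point is worth correcting because it concerns safety surveillance and costs little to correct.

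**What to change.** Reconcile Section 5.3.5.7 and Table 5.1-7 so that both state the same test schedule. If that schedule includes tests between the two visits, add a row for them to Table 5.1-7 and state when kits are dispensed, since no treatment-period table shows dispensing at its final visit.

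In the same edit, check Section 3.5 against Tables 5.1-4 and 5.1-7, and state whether the pregnancy test is kept when a follow-up visit coincides with the Week 24 Post-Study Drug Efficacy Visit. No view is given on which schedule is right.

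The cost is wording in one section and one or two tables, plus extra kits if the reconciled schedule needs them. Home kits are already used in the trial.
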